2. OBJECTIVES

2a. Study Objective

This study aims to develop and evaluate a clinical training intervention utilizing standardized patient actors to improve communication and interpersonal skills of health care workers in caring for HIV infected adolescents (ages 10-24 years), resulting in increased engagement in HIV care.

2b. Specific Aims

Aim 1: To develop patient case scripts specific to adolescent HIV-related care and counseling needs in Kenya, and to establish the number of training interactions necessary to reach competency

Hypothesis: Utilization of real-world adolescent experiences in a simulated patient actor training

program will improve health care provider communication and counseling skills with adolescents in Kenyan HIV care programs

Approach: Case scripts will be developed for male and female SP actors, derived from in-depth interviews with HIV-infected adolescents. We will establish competency scores and pass/fail cut-offs with a pilot sample of 10 health care workers (HCWs).

Aim 2: To assess the impact of SP encounters on the likelihood of adolescent patients retained in HIV care, and adherent to ART at public HIV treatment facilities in Kenya

Hypothesis: SP encounters will increase provider confidence and capacity to facilitate HIV status disclosure and provide supportive interactions with HIV-infected youth, which will significantly increase retention in HIV care and improve ART adherence among adolescents.

Approach: We will utilize a stepped wedge study design to assess retention in HIV services among HIV-infected adolescents. We will compare periods when clinics have received the SP training ('exposed periods') to 'control periods' prior to this training, when clinics are providing standard care. Data will be extracted via electronic medical records.

Aim 3: To estimate the cost-effectiveness of SP training per additional adolescent retained in care and cost-utility per life-year saved and per disability-adjusted life-year (DALY) averted for each adolescent

Hypothesis: An interactive SP training program will be cost-effective

Approach: We will measure detailed healthcare and program costs. We will use these costs to (1) estimate the short-term cost-effectiveness (measured as cost per additional adolescent retained in care) and (2), use modeling methods to estimate the long-term cost utility (measured as cost per disability-adjusted life-year averted).

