An individual who meets any of the following criteria will be excluded from participation in this study: Conditions that would place the individual at increased risk or preclude the individual's full compliance with or completion of the study. This applies both to the pilot phase and the RCT.

Table 2. Inclusion	on Criteria for all P	articipants
--------------------	-----------------------	-------------

Population	Sampling	N	Inclusion Criteria
	Selected from clinics		≥40 adolescents currently in HIV care
Clinic clusters	with ≥40 adolescent clients	24	EMR data system
			No concurrent adolescent interventions
			>18 years of age
Health Care Workers (e.g. doctors, nurses, clinical officers, nurse counselors)	Up to 10 per clinic	240	Employed at trial site in clinical care for at least three months and/or have a 1 year contract (i.e. not temporary staff)
			Provides clinical services to adolescents
Adolescent client records	Complete record audit	Up to 50,000	Records of clients age 10-24 in trial sites
			Ages 10-24
Adolescent clients	escent clients Up to 20 per clinic per time point		Seeking counseling or treatment services at trial site
			HIV-infected

5e. Strategies for recruitment and retention

Pilot phase

Up to 10 HCWs who are >18 years of age, and employed in HIV care at Comprehensive Care Centers (CCCs) and adolescent clinics at KNH will be recruited to participate in the pilot testing of study tools and scoring rubric. We will obtain permission from the clinic directors before recruitment. We will receive a list of potential participants. A member of the study team will be stationed at the clinics and approach potential participants to learn more about the pilot testing phase of the study. In this phase, HCW participants will take part in a pilot 2-3 day training that includes a didactic component, 6-7 SP encounters, group debriefing and discussion. Participants will provide their contact information to ensure completion of the training.

Stepped-wedge randomized controlled trial

Clinics/individual HCW participants: For the stepped-wedge trial, the SPEED study team
will identify up to 24 clinics that meet study eligibility criteria. We will receive permission
from NASCOP and local administrative teams to enroll these clinics. We will then send
letters to administrative teams of the selected clinics. The letter will have information on
the objectives of the SP intervention and will include a formal request for the clinic to be

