In the pilot phase, we will determine the logistics of the training timing and schedule and establish pass/fail cut-off scores for acceptable competency. HCWs will sign standard written informed consent. The pilot phase will consist of the intervention training for 10 HCWs in HIV care at Kenyatta National Hospital. The training will take place over approximately 2-3 days and include didactic and role-playing experiences with the SPs. During the training, provider participants will rotate through up to 7 video-taped SP encounters. Each encounter will last approximately 10-15 minutes. During the encounter, the HCW will counsel the SP as if they were a real client. Encounters will be followed by facilitated group debriefing sessions. The trainer will facilitate discussion and each provider will have the opportunity to discuss their experience and receive feedback from peers and actors. Faculty experts will review and grade the videotapes via an online learning management system. A study team of faculty and experts from Kenya and the US with expertise in adolescent health will provide structured feedback on participants' technical competency according to a faculty checklist.

Training evaluation

At completion of the training session, all HCW participants will complete a training satisfaction survey and a competency survey. Due to COVID-19 pandemic starting March 2020, HCW surveys for Wave 4 will be conducted by phone instead of in-person at a healthcare facility. After the implementation period, about 5 HCWs will be invited to participate in brief exit interviews on relevance of the training to their work, and barriers and facilitators to implementing skills they learned. Exit interviews will be conducted by a study staff member in a private room and last up to 30 minutes.

7b. Stepped Wedge Randomized Controlled Trial (RCT)

We will conduct a stepped wedge randomized controlled trial (RCT) to test the impact of the finalized clinical training intervention on health seeking behaviors of HIV-infected adolescents.

Baseline assessment

At each of the enrolled clinics, we will conduct a baseline assessment of all clinical and satisfaction endpoints, including audits of adolescent client clinical records, and adolescent satisfaction surveys. Facility surveys will be conducted with a clinic representative to assess staffing, training experience, and current services for adolescent HIV care.

Intervention waves

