11. DATA COLLECTION

All data collection tools submitted with this application can be found in the Appendices.

Data sources for HCW participants

- Audio-visual recordings: Video-recordings, locally recorded on a web-camera and uploaded to the SPEED learning management system (LMS), will be made of each HCW-SP interaction for training, scoring, and debriefing/feedback purposes in the pilot and in the RCT. The LMS will utilize Canvas software, a program available only to the Study Team and HCW participants. Each HCW will have a study ID number assigned to them and will log in to the LMS using a user name and private password.
- Surveys:
 - Actor feedback checklist (used in training only): Actors will complete an actor feedback checklist and review it with each HCW during the training.
 - Faculty checklist (used in training only): Faculty experts will review the videos and complete a faculty checklist with a final competency score for each HCW immediately after the training. These scores will be stored with each user record.
 - HCW sociodemographic and satisfaction survey: HCW participants will complete the sociodemographic and satisfaction questions at baseline and in the SPEED training.
 - HCW self-rated competency: HCW participants will complete the competency survey immediately after their training and at the end of each wave to assess perceived competency to care for adolescent patients. The survey will be repeated to assess changes in competency over time during the trial. The final survey will be conducted by telephone due to COVID-19.
 - Exit interviews: A purposeful sample of HCW participants from each wave will take part in one semi-structured exit interview each at the end of the RCT to better understand barriers and facilitators to applying the skills they learned in the SPEED intervention to their routine practice. The interview will follow a structured interview guide.
 - Facility survey: This survey will be administered to a health facility representative at baseline and at the end of each wave of the RCT to capture facility characteristics, including turn-over of SPEED-trained HCWs, patient volume, and any relevant changes in HIV policies and procedures.
- Program records:
 - *Cost data:* Direct and indirect cost data for the CEA/CUA analyses will be obtained from clinic program data (e.g. HCW salaries from employment records)

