Data from the completed faculty checklists will be used to establish competency scores. Participants, faculty experts, and actors will be asked to provide qualitative feedback on the checklist indicators. Inter-rater reliability of the faculty checklist will be determined using Cohen's kappa. We will assess correlation of checklist variables and utilize principal component analysis to reduce the number of variables, using a scree test method to plot eigenvalues. Pass/fail cutoff scores will utilize relative and absolute standard-setting processes [33]. In relative processes, initial pass/fail determinations will depend on the performance of the cohort, such that all scoring less than 1 standard deviation below the mean receives a fail. Relative standards are useful with new trainings where there is no prior performance data. Subsequently we will explore standard-setting using an iterative combination of the Angoff item-based method and the Hofstee whole-test method. The Angoff method establishes the probability of a borderline student to accomplish each item on the checklist. The sum of probabilities across items is then equal to a passing score. A team review process is convened in which reviewers discuss outlier ratings, assess performance data after pilot testing, and revision of ratings if necessary. The Hofstee whole-test method combines normative and absolute judgments, in that checklist reviewers make four determinations: the minimum and maximum acceptable passing scores. and the minimum and maximum proportions of students failing. A final cut-off determination will be made by averaging the Hofstee and Angoff scores.

Stepped-Wedge Randomized Controlled Trial

The primary analysis will be an intent-to-treat (ITT) analysis, assuming that adolescents who receive care at clinics after the SPEED training will be 'exposed' to HCWs trained in the SPEED intervention until the end of the study.

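### The faculty checklist is to be reduced by principal component analysis on a pilot of at most 10 health care workers, so the item set or weights behind the competency score are likely to be unstable.

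*Combined protocol and SAP*

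**What the plan says.** Section 12c, pilot phase, uses the completed faculty checklists to establish competency scores. After looking at item correlations, the team will "utilize principal component analysis to reduce the number of variables, using a scree test method to plot eigenvalues". Cohen's kappa is planned for inter-rater reliability, and "Participants, faculty experts, and actors will be asked to provide qualitative feedback on the checklist indicators". An Angoff and Hofstee procedure with team review then sets the pass mark.

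On sample size, section 7a states: "The pilot phase will consist of the intervention training for 10 HCWs in HIV care at Kenyatta National Hospital". The recruitment text in section 5e makes that a ceiling: "Up to 10 HCWs who are >18 years of age". On the amount of data per person, section 7a adds: "During the training, provider participants will rotate through up to 7 video-taped SP encounters", and "Faculty experts will review and grade the videotapes via an online learning management system". Section 11 describes one result per person: faculty "complete a faculty checklist with a final competency score for each HCW immediately after the training".

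The score is used in Aim 2. Sections 3b and 12c list the pass proportion per clinic before and after training, the association of competency with adolescent satisfaction, and the association of competency with care outcomes.

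The plan does not give the number of checklist items, whether the row of the analysis is an HCW or an encounter, a retention rule beyond the scree plot, a stability check, or a repeat of the analysis in trial data.

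**The concern.** Principal component analysis works from the item correlation matrix, and 10 people estimate that matrix very poorly. If the analysis decides which items stay, or how they are weighted, part of that decision reflects chance in one small group from a single hospital. The result is then carried into a trial of up to 240 HCWs.

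What is at stake is the reliability of the competency score. A less reliable score pulls its associations with satisfaction and care outcomes towards zero. The item set also enters the pass mark, because the Angoff mark is a sum over items. The trial's own faculty checklists offer a much larger base for the same analysis.

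**Working it through.** The plan gives no precision figure for this analysis, so there is nothing to reproduce.

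**Inputs from the protocol.** At most 10 pilot HCWs (sections 5e, 7a). Up to 7 graded encounters each, so at most 10 × 7 = 70. Up to 10 HCWs in each of 24 clinics, so up to 240 in the trial (section 5, Table 2).

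**Assumptions, not in the protocol.** 20 items unless stated; one common factor; continuous items unless stated; the half of the items with the largest absolute first-component loadings is kept. The protocol states no such rule. It stands in for any data-driven reduction.

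**1. Precision of one correlation.** 95% interval = tanh(atanh r ± 1.96/√(n − 3)).
- n = 10, r = 0: 1.96/√7 = 0.741, giving −0.63 to 0.63.
- n = 10, r = 0.3: −0.41 to 0.78.
- n = 240, r = 0.3: 0.18 to 0.41.

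With one row per HCW the matrix has rank at most 10 − 1 = 9, whatever the number of items.

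**2. Unrelated items (simulation).** At n = 10 the first component takes on average 24% of the variance and the first three 59%. At n = 240 the figures are 8% and 22%.

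**3. Which items survive, one row per HCW (simulation, loadings spread evenly over 0.2 to 0.8).**

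| | n = 10 | n = 240 |
|---|---|---|
| Best items kept (chance 50%) | about 70% | about 95% |
| Agreement between two samples | about 61% | about 92% |

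If the items are scored yes/no, n = 10 gives about 63% and 55%.

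**4. Encounters as rows.** Effective n = 70/(1 + 6 × ICC), where the ICC is the within-HCW correlation. The last column has half the items at loading 0.5 and half at zero.

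| ICC | Effective n | Best items kept, loadings 0.2–0.8 | Best items kept, half at 0.5 |
|---|---|---|---|
| 0.3 | 25 | 86% | 90% |
| 0.5 | 17.5 | 83% | 80% |
| 0.8 | 12.1 | 76% | 66% |

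At loadings 0.2 to 0.8 the agreement between two pilots is still only 63% to 80%. Averaging the 7 encounters per HCW before the analysis gains almost nothing over one row per HCW.

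**5. Effect on the score.** For an unweighted sum of the kept items, correlation with true competency = Σλ / √[(Σλ)² + Σ(1 − λ²)]. Example with 10 items at 0.5 and 10 at zero:
- the right ten items: 5/√(25 + 7.5) = 0.88
- all twenty items: 5/√(25 + 7.5 + 10) = 0.77

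Averaged over simulated selections:

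| True loadings | Selected at n = 10 | Selected at n = 240 | Full checklist | Loss, n = 10 v n = 240 |
|---|---|---|---|---|
| 0.2 to 0.8 | 0.92 | 0.94 | 0.935 | about 2% |
| 0.1 to 0.6 | 0.80 | 0.86 | 0.86 | about 7% |
| half 0.5, half 0 | 0.72 | 0.88 | 0.77 | about 18% |

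Selecting on yes/no items lowers the n = 10 figures in the last two rows to about 0.78 and 0.67 (losses of about 9% and 24%).

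**The case against.** The strongest reply is that the analysis is neither as small nor as decisive as it looks. Faculty grade up to 70 videos, and with encounters as rows and strong items the selection is good: with half the items at loading 0.7 and half at zero, 98% to 100% of the right items are kept at an ICC of 0.5 or 0.3. Reducing the number of variables may mean forming components rather than deleting items. Qualitative feedback and kappa also bear on the checklist, and the pass mark rests mainly on expert judgement. When all items measure the same thing, swapping one for another costs only about 2% of the score's correlation with true competency.

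Much of this stands, and it rules out two stronger readings.

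- A reader might infer that the items are chosen largely by noise. That is close to true only with one row per HCW and moderate or weak loadings. The protocol fixes neither the unit nor the deletion rule, and it names other inputs. Nor does a scree plot of noise always show a dominant first component: in step 2 the second and third average (59 − 24)/2 = 17.5% each, a gradual decline from 24%.
- A reader might infer that a null mechanism result would be an artefact of the score. A 2% loss could not produce that. A loss near 20% would weaken an association, but the documents do not show that the checklist is of that kind.

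Three parts of the reply do not stand. The plan never says that encounters are the unit, and section 11 describes one final score per HCW. Component weights from 10 people are estimated from the same poorly known correlations as a list of retained items. Nothing says that qualitative feedback overrides the component analysis.

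Timing is a fair point. The pilot belongs to year one (section 8) and this version is dated May 2020, so items may already have been removed. The remedy has to allow for that.

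**Conclusion.** The concern holds in a limited form. A reduction based on at most 10 independent people is likely to be unstable, and the plan has no safeguard against carrying that instability into the trial. With one row per HCW, about 70% of the best items are kept and two pilots agree on about 61%. With up to 70 encounters as rows, performance ranges from modest to good depending on the ICC.

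The cost to the competency score, compared with selection on 240 HCWs, runs from about 2% to roughly 20% of its correlation with true competency. Where half the items are uninformative, the full checklist would do only somewhat better than the pilot selection (0.77 against 0.72). So most of the gain there comes from a well-founded reduction, and less from simply keeping everything.

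These sizes rest on assumed item counts, loadings, ICCs and a keep-half rule. The figures for 240 are a best case, because HCWs are clustered in clinics. At an assumed clinic ICC of 0.1 the effective number is 240/(1 + 9 × 0.1) = 126, still far above 10.

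The exposure is confined to the pass proportion per clinic and the competency associations. Retention comes from electronic medical records (section 12a) and is not affected.

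**What to change.** In section 12c:

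1. Call the pilot component analysis descriptive. Do not delete or weight checklist items on it; keep items on content and expert review.
2. Run the item reduction on the trial faculty checklists (up to 240 HCWs), using between-HCW correlations, allowing for clustering by clinic, and replacing the scree test with parallel analysis. Do this blind to the satisfaction and retention outcomes, so that the score cannot be tuned to them. State the number of items, the unit of analysis and the retention rule.
3. If items have already been dropped, repeat the analysis on the items as scored in the trial, and report the competency associations under both item sets as a sensitivity analysis.

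The pilot-based Angoff and Hofstee procedure for the pass mark can stay.

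Cost: SAP wording, one re-analysis and possibly a longer checklist for faculty to score. No new participants are needed and the training does not change.
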